### **5.5.2 Other Restrictions and Precautions**

#### **5.5.2.1 Immunizations**

There is limited information available regarding the effectiveness of immunizations in non-human primates and humans that have been treated with abatacept. Limited data are available on the effect of therapeutic vaccinations in subjects receiving abatacept.

Due to the risk of infection, vaccination of subjects with any live vaccine is absolutely contraindicated during the treatment phase of the study (that is, at any time after entry into the induction period), as is the administration of LIVE oral polio vaccine to household contacts. The Centers for Disease Control and Prevention Advisory

Committee on Immunization Practices (CDC-ACIP) recommends that subjects should not be administered a live virus vaccination for at least 3 months after discontinuing high-dose corticosteroid therapy (defined as more than 20 mg of prednisone per day for more than 2 weeks). In view of the long half-life of abatacept, study subjects should not be administered a live virus vaccine for a minimum of 3 months following the last dose of abatacept.

## **5.6 Treatment Compliance**

Compliance will be documented via the use of patient diaries to record the date and time of self-administration of medication at home. Study drug reconciliation will be performed at each visit during the treatment period.

## **6 STUDY ASSESSMENTS AND PROCEDURES**

### **6.1 Time and Events Schedule**

The Time and Events Schedule (Section 6, Table 3) summarizes the frequency and timing of various measurements.

#### Pre-screening procedures

Written informed consent will be obtained for this study by the principal investigator or his/her designee from all patients prior to any protocol-specific procedures. The study will be conducted in accordance with the Food and Drug Administration (FDA) approved revision of the Declaration of Helsinki, current FDA regulations, and International Conference on Harmonization (ICH) guidelines.

#### Procedures Performed Prior to Treatment Screening (Day -28 to -1):

The following screening evaluations will be performed within 4 weeks prior to enrollment:

- Informed consent, inclusion/exclusion criteria, prior concomitant medications
- Medical history, physical examination, including a dermatological exam
- Vital signs, body weight
- Assessments of disease severity will be conducted including SALT (Severity of Alopecia Tool)
- Physician's global assessment (PGA)
- Clinical laboratory evaluation (complete blood count, basic metabolic profile, hepatic panel and urinalysis), hepatitis B and C screening panel, HIV test, lipid profile, serum pregnancy test
- Tuberculosis testing (PPD skin test or quantiferon test)
- Chest X ray

A visit will be scheduled 48-72 hours after placement of the PPD for reading of the test results. If possible, this visit will be combined with the baseline visit. The results of all assessments/tests listed above must be reviewed prior to enrollment to ensure that the patient meets entry criteria and that no exclusion criteria are present.

#### Baseline (Day 0) Procedures Performed Prior to treatment

- Review of inclusion/exclusion criteria
- Vital signs, body weight
- Adverse events reporting, concomitant medication review
- Photography
- Physician evaluation utilizing the PGA and SALT scale
- Patient global assessment and quality of life assessment
- Urine pregnancy testing for WOCBP

- Blood collection for immunological studies including assessment of presence or absence of AA GWAS risk haplotype
- Scalp biopsy (4mm punch biopsy)
- Training of subject in Subcutaneous administration of medication followed by observed patient self-administration of medication

#### Weeks 4, 8, and 12 (Days 28, 56 and 84)

Visit days will have an acceptable window of  $\pm 3$  day.

- Vital signs, body weight
- Adverse events reporting, concomitant medication review
- Photography
- Physician evaluation utilizing the PGA and SALT scale
- Patient global assessment and quality of life assessment (week 12 only)
- Urine pregnancy testing for WOCBP
- Physical and dermatological examination (week 12 only)
- Clinical laboratory evaluation (only weeks 4 and 12)
- Scalp biopsy (4mm punch biopsy) (only weeks 4 and 12)
- Blood collection for immunological studies (only weeks 4 and 12)
- Optional Scalp biopsy (4mm punch biopsy) in addition to weeks 4 and 12 – at the discretion of the investigator and with the consent of the subject, based upon perceived utility in context of individual patient response to therapy and durability of that response.
- Optional Blood collection for immunological studies in addition to weeks 4 and 12, at the discretion of the investigator and with the consent of the subject.
- Training/reinforcement of training for self-administered SQ injection
- Patient observed self-administering study medication

#### Week 18 (Day 126 $\pm$ 1)

- Vital signs, body weight
- Adverse events reporting, concomitant medication review
- Photography
- Physician evaluation utilizing the PGA and SALT scale
- Urine pregnancy testing for WOCBP
- Optional Scalp biopsy (4mm punch biopsy) - at the discretion of the principal investigator and with the consent of the subject, based upon perceived utility in context of individual patient response to therapy.
- Optional Blood collection for immunological studies, at the discretion of the principal investigator and with the consent of the subject.
- Training/reinforcement of training for self-administered SQ injection
- Patient observed self-administering study medication

#### Week 24 (Day 168 $\pm$ 7) – End of Treatment

- Vital signs, body weight
- Physical and dermatological examination
- Adverse events reporting, concomitant medication review
- Photography
- Physician evaluation utilizing the PGA and SALT scale
- Patient global assessment and quality of life assessment
- Urine pregnancy testing for WOCBP
- Clinical laboratory evaluation
- Scalp biopsy (4mm punch biopsy)
- Blood collection for immunological studies

Weeks 36 and 48 (Days 252 and 336  $\pm$ 7 days) – Observational Period

- Vital signs, body weight
- Physical and dermatological examination (only week 48)
- Adverse events reporting, concomitant medication review
- Photography
- Physician evaluation utilizing the PGA and SALT scale
- Patient global assessment and quality of life assessment
- Optional Scalp biopsy (4mm punch biopsy) – at the discretion of the principal investigator and with the consent of the subject, based upon perceived utility in context of individual patient response to therapy and durability of that response.
- Optional Blood collection for immunological studies, at the discretion of the principal investigator and with the consent of the subject.

Weeks 30, 36, 42, 48 (Extension Option)

Visit days will have an acceptable window of  $\pm$ 7 days.

- Vital signs, body weight
- Adverse events reporting, concomitant medication review
- Photography
- Physician evaluation utilizing the PGA and SALT scale
- Patient global assessment and quality of life assessment
- Urine pregnancy testing for WOCBP
- Physical and dermatological examination (week 36)
- Clinical laboratory evaluation, if indicated (at 12 weeks after end of study treatment)
- Optional Scalp biopsy (4mm punch biopsy) – at the discretion of the investigator and with the consent of the subject, based upon perceived utility in context of individual patient response to therapy and durability of that response.
- Optional Blood collection for immunological studies in addition to weeks 4 and 12, at the discretion of the investigator and with the consent of the subject.

### Weeks 40 to 72 (Observational Period after Extension Option)

Visit days will have an acceptable window of  $\pm 7$  days.

- Patient will be observed at 12 and 24 weeks after completing study medication
- Vital signs, body weight
- Physical and dermatological examination (at end of study)
- Adverse events reporting, concomitant medication review
- Photography
- Physician evaluation utilizing the PGA and SALT scale
- Patient global assessment and quality of life assessment
- Optional Scalp biopsy (4mm punch biopsy) – at the discretion of the principal investigator and with the consent of the subject, based upon perceived utility in context of individual patient response to therapy and durability of that response.
- Optional Blood collection for immunological studies, at the discretion of the principal investigator and with the consent of the subject.

### Early Termination

- Vital signs, body weight
- Physical and dermatological examination
- Adverse events reporting, concomitant medication review
- Photography
- Physician evaluation utilizing the PGA and SALT scale
- Patient global assessment and quality of life assessment
- Clinical laboratory evaluation
- Optional Scalp biopsy (4mm punch biopsy) - at the discretion of the principal investigator and with the consent of the subject, based upon perceived utility in context of individual patient response to therapy.
- Optional Blood collection for immunological studies, at the discretion of the principal investigator and with the consent of the subject.
- The reason for early withdrawal/study drug discontinuation must be documented

### Unscheduled Visits

An unscheduled visit can occur at any time during the study. A source document must be maintained for these unscheduled visits. The date for the visit and any data generated must be recorded on the appropriate CRF. At treatment discontinuation/early termination subjects will undergo study evaluations per the Schedule of Assessments.

### Duration of Treatment

Treatment will be continued for 6 months to provide adequate time to assess the short-term efficacy and safety of abatacept in patients with alopecia areata. Patients will then be followed for an additional 6 months to assess the timing and incidence of relapse of AA.

### **6.1.1 Study Completion or Early Discontinuation Visit**

At the time of study early withdrawal, the reason for early withdrawal and any new or continuing adverse events should be documented.

### **6.1.2 Study Drug Discontinuation**

If study drug administration is discontinued, the reason for discontinuation will be recorded.

Table 3: Schedule of Assessments

| Visit   | Screening | PPD reading | Base-line      | Week 4 | Week 8           | Week 12 | Week 18          | Week 24/ET | Week 30, 36, 42, 48 (optional) | 12 Weeks after end tx | 24 Weeks after end tx |
|---|-----------|-------------|----------------|--------|------------------|---------|------------------|------------|--------------------------------|-----------------------|-----------------------|
| Day   | -28 to -1 |             | 0              | 28±1   | 56±1             | 84±1    | 126±1            | 168±7      |                                |                       |                       |
| Informed Consent  | X         |             |                |        |                  |         |                  |            |                                |                       |                       |
| Inclusion/Exclusion Criteria  | X         |             | X              |        |                  |         |                  |            |                                |                       |                       |
| Medical History   | X         |             |                |        |                  |         |                  |            |                                |                       |                       |
| Body Weight   | X         |             | X              | X      | X                | X       | X                | X          | X                              | X                     | X                     |
| Physical/Cutaneous Exam   | X         |             |                |        |                  | X       |                  | X          |                                |                       | X                     |
| Vital Signs   | X         |             | X              | X      | X                | X       | X                | X          | X                              | X                     | X                     |
| Concomitant Medications   | X         |             | X              | X      | X                | X       | X                | X          | X                              | X                     | X                     |
| Adverse events  |           |             | X              | X      | X                | X       | X                | X          | X                              | X                     | X                     |
| Photography   |           |             | X              | X      | X                | X       | X                | X          | X                              | X                     | X                     |
| SALT evaluation   | X         |             | X              | X      | X                | X       | X                | X          | X                              | X                     | X                     |
| Physician global assessment   | X         |             | X              | X      | X                | X       | X                | X          | X                              | X                     | X                     |
| Patient quality of life assessment  |           |             | X              |        |                  | X       |                  | X          | X                              | X                     | X                     |
| Patient global assessment   |           |             | X              |        |                  | X       |                  | X          | X                              | X                     | X                     |
| Clinical laboratory evaluation*   | X         |             |                | X      |                  | X       |                  | X          | X                              |                       |                       |
| Hepatitis screening panel, HIV test   | X         |             |                |        |                  |         |                  |            |                                |                       |                       |
| Lipid Profile   | X         |             |                |        |                  |         |                  |            |                                |                       |                       |
| PPD test and reading  | X         | X           |                |        |                  |         |                  |            |                                |                       |                       |
| Serum pregnancy test  | X         |             |                |        |                  |         |                  |            |                                |                       |                       |
| Urine pregnancy test  |           |             | X              | X      | X                | X       | X                | X          | X                              |                       |                       |
| Scalp Biopsy  |           |             | X              | X      | (X) c | X       | (X) c | X          | (X) c               | (X) c      | (X) c      |
| Phlebotomy for immunological studies  |           |             | X d | X      | (X) c | X       | (X) c | X          | (X) c               | (X) c      | (X) c      |
| Training/reinforcement of training for self-administered SQ injection
Patient observed self-administering study medication |           |             | X b | X      | X                | X       | X                | X          | X                              |                       |                       |
| Chest X ray-1 view  | X         |             |                |        |                  |         |                  |            |                                |                       |                       |

aClinical laboratory evaluation consists of CBC, BMP, hepatic panel, and urinalysis. Additional evaluations will only be performed if needed to verify normalization of previously abnormal lab values.

bBaseline dose will be subcutaneous administration of abatacept.

c Optional additional Scalp biopsies (4mm punch biopsy) may be performed at the discretion of the investigator and with the consent of the subject, based upon perceived utility in context of individual patient response to therapy and durability of that response. Optional Blood collection for immunological may be performed at the discretion of the investigator and with the consent of the subject.

d Includes testing for AA GWAS risk haplotype

## **6.2 Study Materials**

Bristol-Myers Squibb (BMS) will provide abatacept and laboratory testing at no cost for this study.

## **6.3 Safety Assessments**

Analysis of safety is included as a secondary endpoint. All subjects who receive a dose of abatacept will be evaluated for safety. Safety outcomes include adverse events, clinically significant changes in vital signs, laboratory test abnormalities, and clinical tolerability of the drug. The investigator will determine the severity of each adverse event as mild, moderate, severe, or very severe. Laboratory findings that the investigator feels are clinically relevant should be recorded as adverse events. In addition, the investigator will determine the relationship of the adverse event to the administration of the study drug. Any occurrence of a SAE from time of consent forward, up to and including follow-up visits will be reported. See Section 6.5 for the SAE reporting procedures.

### **6.3.1 Physical Examinations**

During the treatment period, the physical examination is to be performed before administration of abatacept. While the interim physical examination may not be as comprehensive as the complete physical examination, important body systems should be included as deemed clinically indicated by the investigator. These body systems may include lymph nodes, liver, spleen, and breast. An interim physical examination may note any changes in the subject's condition since the last assessment and does not preclude examination of any of the body systems as clinically indicated.

### **6.3.2 Tuberculin Skin Testing**

A tuberculin skin test (PPD test: purified protein derivative tuberculosis skin test) should be performed and interpreted according to the applicable local Health Authority and/or Medical Society guidelines (those that provide recommendations for tuberculin skin testing for subjects who are to receive biologics, who are immunosuppressed, who have a prior history of BCG

vaccinations(viii,ix), or who have a prior positive test). Tuberculin skin testing is not contraindicated for persons who have been vaccinated with BCG.

QuantiFERON® testing is an acceptable alternative when tuberculin skin testing is not appropriate. A tuberculin skin test is not required if one was performed within 6 months of screening and documentation of testing is on file. If tuberculin skin testing is performed at screening, then the 72-hour reading must be completed before administration of abatacept.

## **6.4 Efficacy Assessments**

### **6.4.1 Primary Efficacy Assessment**

The study's *primary efficacy endpoint* will be the proportion of responders after 6 months of treatment, with response defined as 50% or greater hair re-growth from baseline as assessed by SALT score (Figure 6) at week 24. Treatment may be extended by up to an additional 6 months beyond the initial 6 months of treatment if clinically indicated at the discretion of the investigator.

This is a relatively strict definition for defining responders and non-responders and was chosen to minimize the potential for spontaneous remission, in which fewer than 10% are expected to achieve this magnitude of hair regrowth spontaneously.

SALT – Severity of Alopecia Tool

A. The proportion of scalp involvement is determined by dividing the scalp into 4 quadrants and estimating the percentage of the scalp surface that all the alopecic areas would occupy if placed together. The following groups will be used:

S: Scalp hair loss

- |                              |                              |
|------------------------------|------------------------------|
| _____ S0 = No hair loss      | _____ S4 = 76%-99% hair loss |
| _____ S1 = <25% hair loss    | _____ a = 76%-95% hair loss  |
| _____ S2 = 26%-50% hair loss | _____ b = 96%-99% hair loss  |
| _____ S3 = 51%-75% hair loss | _____ S5 = 100% hair loss    |

Body hair loss

- B0 = No body hair loss  
 B1 = some body hair loss  
 B2 = total (100%) body hair loss

Nail involvement

- N0 = No nail involvement  
 N1 = some nail dystrophy  
 N1a = 20 nail dystrophy

[figure not shown]
Percentage change from baseline (% regrowth) =  

$$\frac{[(SALT\ BL - SALT\ F/U) / SALT\ BL] \times 100\%}{}$$
absolute change from baseline  

$$\frac{SALT\ BL - SALT\ F/U}{}$$
absolute change from BL

**6.4.2 Secondary Efficacy Assessments**

As secondary endpoints, efficacy will be measured by changes in hair re-growth as a continuous variable as determined by physical exam and Canfield photography, as well as patient and physician global evaluation scores. To assess the durability of responses, patients will continue to be followed for an additional 6 months off treatment. To assess the durability of response and the incidence of relapse, patients who achieve 50% regrowth from baseline (50% reduction in baseline SALT score) will continue to be followed for an additional 6 months off treatment or until it is determined that relapse has occurred. Relapse will be defined as any

[figure not shown]

**Figure 6. SALT score.** The percentage of hair loss in any one of the four views (areas) of the scalp = the percentage hair loss x percent surface area of the scalp in that area. The SALT score then equals the sum of the scalp hair loss in each area.

(a) Top (left side view) = 95% x .18 = 17.1

(b) Second (right side view) = 90% x .18 = 16.2

(c) Third (top of scalp) = 95% x .40 = 38 (realizing that most of hair loss is probably male pattern hair loss)

recurrence of hair loss in responders (subjects achieving greater than 50% decrease in SALT score from baseline during the first 6 mths of the study) who had achieved stable regrowth without continued loss for at least 2 mths; and loss of  $\geq 25\%$  of regrowth in patients who had achieved 50% regrowth during treatment but still had chronic low grade hair loss. Nonresponders to 6 months study treatment (defined as failure to achieve 50% improvement in SALT score compared to baseline) will not be required to participate in the 6mth follow-up period.. Partial responders will continue to be followed to assess for delayed achievement of complete response. Analysis of safety is included as a secondary endpoint. All subjects who receive a dose of abatacept will be evaluated for safety.

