|   | 
lack of existing evidence-based data for any treatment in alopecia areata, there is a strong rationale for testing CTLA4-Ig treatment in this disease.
  |
| 
Study Objectives:
 Primary:
 Secondary:
             | 
The study's primary efficacy endpoint will be the proportion of responders after 6 months of treatment, with response defined as 50% or greater hair re-growth from baseline as assessed by SALT score at week 24. This is a relatively strict definition for defining responders and non-responders and was chosen to minimize the potential for spontaneous remission, in which fewer than 10% are expected to achieve this magnitude of hair regrowth spontaneously.
 
As secondary endpoints, efficacy will be measured by changes in hair re-growth as a continuous variable as determined by physical exam and Canfield photography, as well as patient and physician global evaluation scores. To assess the durability of responses, patients will continue to be followed for an additional 6 months off treatment or until it is determined that relapse has occurred. Additionally, patient reported outcomes, safety measures, incidence and timing of relapse will be important secondary outcomes. We will also explore the efficacy of treating 2 patients with current alopecia totalis or universalis, and in doing so, will compare, on an exploratory basis, the rate of occurrence of hair regrowth in patients with moderate to severe patch type alopecia areata compared to those with current alopecia totalis or universalis.
 
In addition, response to abatacept treatment will be examined on an exploratory basis for correlation with the presence or absence of the AA GWAS risk haplotype.
 |
| 
Study Design:
   | 
Open label pilot study of 6 months of abatacept 125mg SC per week in the treatment of moderate to severe AA and current alopecia totalis or universalis, followed by 6 months follow-up off drug to assess the incidence and timing of recurrence of disease. Treatment may be extended by up to 6 additional months beyond the initially planned 6 months of treatment if clinically indicated at the discretion of the investigator.
  |

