### **Week 25 to 48 (follow-up period off study medication)**

All patients will be seen at week 36 and 48, after completion of 6 months of study drug, to determine durability of response or evidence for a delayed effect. Importantly patients who achieved  $\geq$  50% regrowth as measured by SALT score (responders) will be seen at week 36,

and 48 after end of study treatment in order to assess the frequency and timing of relapse or to capture the occurrence of further regrowth.

Relapse will be defined as any recurrence of hair loss in responders (subjects achieving greater than 50% decrease in SALT score from baseline during the first 6 months of the study) who had achieved stable regrowth without continued loss for at least 2 months; and loss of  $\geq$  25% of regrowth in patients who had achieved 50% regrowth during treatment but still had chronic low grade hair loss.

Nonresponders will also continue follow-up in order to assess for delayed response.

Efficacy evaluations: SALT, PGA, Patient global assessment and patient quality of life assessment will be performed at Weeks 36, and 48.

Blood draws for safety parameters will be conducted at week 30 if deemed necessary to assess normalization of any previously abnormal values.

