### Duration of Treatment

After the screening period, subjects will begin weekly self-administered subcutaneous abatacept and will continue treatment for 6 months. Patients will be instructed in self-administration of study medication at baseline (week zero) and will be observed self-administering medication at each visit. Instructions regarding study drug administration will be reinforced as needed.

The 6-month treatment period is expected to provide adequate time to assess the short-term efficacy and safety of abatacept in patients with moderate to severe AAP. Responders will then be followed for 6 months off drug.

Treatment may be extended by up to an additional 6 months beyond the initial 6 months of treatment if clinically indicated at the discretion of the investigator.

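### Section 6.4.2 exempts nonresponders from the 6-month follow-up and ends responder follow-up at relapse, while Section 4.1 sees all patients at weeks 36 and 48; with no efficacy set or missing-data rule, who is measured can depend on outcome

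*Combined protocol and SAP*

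**What the plan says.** The combined protocol and SAP describes post-treatment follow-up in several places that do not agree.

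- **Section 6.4.2** defines nonresponders as those below 50% SALT improvement after 6 months and says that they "will not be required to participate in the 6mth follow-up period". It then adds: "Partial responders will continue to be followed to assess for delayed achievement of complete response". The term partial responder is not defined.
- **Synopsis, Study Objectives**: "patients will continue to be followed for an additional 6 months off treatment or until it is determined that relapse has occurred". Sections 2.1 and 6.4.2 attach the same end at relapse to patients who reached 50% regrowth.
- **Section 4.1, Week 25 to 48**: "All patients will be seen at week 36 and 48, after completion of 6 months of study drug", and further "Nonresponders will also continue follow-up in order to assess for delayed response".
- **Section 4.1, Duration of Treatment**: "Responders will then be followed for 6 months off drug". It is silent on nonresponders.
- **Section 6.1 visit list and Table 3**: the week-36 and week-48 visits, and the Table 3 columns headed "12 Weeks after end tx" and its 24-week counterpart, include SALT and the global and quality-of-life measures. Neither place limits them by response.
- **Sections 2.2 (opening paragraph), 5.3 and 6.1 (Duration of Treatment)** follow patients for 6 further months with no condition on response or relapse.

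Sections 6.4.2 and 7.3 list group endpoints at weeks 36 and 48: percent regrowth, responder proportion against the historical placebo rate (below 10%), a coverage endpoint, physician and patient global scores, and quality of life. Section 7.2, although titled as analysis populations, contains only accrual text. Section 7.4.2 states who is evaluated for safety. Section 7.4.3 plans proportions and means, with no efficacy denominator and no rule for missing values.

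**The concern.** Section 6.4.2 and the week 25 to 48 text of Section 4.1 cannot both govern. If the site follows 6.4.2, a subject's chance of being measured after week 24 depends on the week-24 outcome and, for responders, on relapse. If the analyst then summarises whoever was measured, the week-36 and week-48 proportions and means describe a selected group, yet the endpoint lists present them as results for the whole group.

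Three things are at stake. The responder proportion compared with the historical rate would tend to read too high when nonresponders are absent. Delayed response, which Section 4.1 gives as a reason for following nonresponders, goes unmeasured at the scheduled visits in those who leave. And the summaries are meant to inform the design of later trials (Section 7.4.3), where an inflated durability estimate would carry over.

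**Working it through.** **1. The plan's own figure.** Section 7.1 gives 80.7% power for n = 15, 10% against 40%, alpha 5%, without naming the test. The two-sided arcsine approximation gives Φ(2(asin√0.4 − asin√0.1)√15 − 1.96) = Φ(2.81 − 1.96) = 80.3%. The two-sided normal approximation with continuity correction gives 81.8%. The stated figure is therefore consistent with standard approximations. It concerns week 24 and does not depend on the follow-up rule.

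**2. Inputs for weeks 36 and 48.** From the documents: 15 subjects, and response at 50% regrowth. The documents give no attendance, relapse or delayed-response rate, so these are assumptions: 6 of 15 respond at week 24 (the design's 40%), 2 of the 6 relapse, none of the 9 nonresponders responds late, and nobody takes the extension. Let s be the number of nonresponders who attend.

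**3. Effect of the nonresponder exemption alone.** Both relapsers are below 50% but are measured. The rate in all treated is 4/15 = 26.7%. The observed-case rate is 4/(6 + s). For means, assume regrowth of 75% if sustained, 40% if relapsed and 15% in nonresponders. The all-treated mean is (4×75 + 2×40 + 9×15)/15 = 515/15 = 34.3%, and the observed-case mean is (380 + 15s)/(6 + s). Bounds for the all-treated rate, with the absent counted first as failures and then as responders, run from 4/15 to (4 + 9 − s)/15.

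| s of 9 attend | Observed rate | Observed mean regrowth | Bounds for all 15 |
|---|---|---|---|
| 9 | 4/15 = 26.7% | 515/15 = 34.3% | 26.7% |
| 6 | 4/12 = 33.3% | 470/12 = 39.2% | 26.7% to 46.7% |
| 3 | 4/9 = 44.4% | 425/9 = 47.2% | 26.7% to 66.7% |
| 0 (extreme) | 4/6 = 66.7% | 380/6 = 63.3% | 26.7% to 86.7% |

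With 4 responders, 2 relapses and 11 nonresponders instead, the all-treated rate is 2/15 = 13.3%. The observed rate is 2/7 = 28.6% with 3 nonresponders attending and 2/10 = 20% with 6.

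**4. Effect of stopping at relapse alone.** All 9 nonresponders attend, and both relapsers leave before the visit in question. If the relapsers are below 50%, the rate moves from 4/15 = 26.7% to 4/13 = 30.8%. Relapse includes any renewed loss after stable regrowth, or loss of a quarter of regrowth, so a relapser may still be a responder: 80% regrowth less a quarter is 60%. If both are still at or above 50%, the rate moves from 6/15 = 40% down to 4/13 = 30.8%. The direction is not fixed. A relapse first documented at week 36 has a SALT score at that visit, so this mechanism bears mainly on week 48.

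**5. Limit of a simple repair.** Counting missing as non-response over all 15 removes the upward shift in proportions. If 2 of the nonresponders who leave would have responded late, however, it reads 4/15 = 26.7% where full follow-up would give 6/15 = 40%. It does nothing for the means.

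**The case against.** The strongest reply is that 6.4.2 permits attendance rather than forbidding it, and that it keeps partial responders. If that term means any regrowth short of 50%, many nonresponders would be retained. This stands against the extreme row (none attend), which should be read as a limit and not as an expectation. It does not remove the conflict: a subject below 50% meets the nonresponder definition and, on that reading, is both exempt and kept.

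Other text softens the loss of information. Section 4.1 provides monthly telephone contact in the observational phase with unscheduled visits if needed, and 6.1 has a SALT evaluation at early termination. Neither replaces a week-36 or week-48 SALT score in someone who has left. The Synopsis and 7.1 express the expected placebo response as a count out of 15, which suggests an all-enrolled denominator for the primary endpoint, but this is a planning remark and does not reach weeks 36 and 48.

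Releasing nonresponders may also be deliberate, since 5.5.1 prohibits other hair-growth treatments for the whole study. That is a reason for the sponsor to reconcile the sections openly; it does not make them agree.

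A reader might go further and infer a 100% week-48 rate, or a relapse frequency of 0/4 because relapsers were not followed for the full 6 months. The first needs every nonresponder to stay away and every relapser to leave before the visit. The second needs the analyst to drop every early relapser from a relapse endpoint, when the wording more naturally names the observation period. The documents support neither.

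**Conclusion.** The contradiction between 6.4.2 and 4.1 is in the current text and should be corrected. The bias is conditional: it arises if 6.4.2 is followed and observed cases are summarised, and the plan does not rule out such a summary. Under the assumed 6 responders and 2 measured relapsers below 50%, the rate reads 33.3% to 44.4% when 6 or 3 of 9 nonresponders attend, against 26.7% in all treated. Optional nonresponder follow-up tends to inflate proportions and means; the stop at relapse can move the rate either way. No attendance figure in the documents fixes the size.

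It would be wrong to infer that the primary result is compromised. The week-24 endpoint precedes the follow-up conflict, although it too has no stated missing-data rule. The affected endpoints are secondary and descriptive in an exploratory pilot.

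A related ambiguity has no size attached: several week-36 and week-48 items in 2.2, 6.4.2 and 7.3 use calendar weeks, when a subject on extended treatment may still be on drug, whereas Table 3 and the extension text in 4.1 and 6.1 count 12 and 24 weeks from end of treatment.

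**What to change.** 1. **Follow-up.** Reconcile the Synopsis, 2.1, 4.1 (Duration of Treatment) and 6.4.2 with the week 25 to 48 text of 4.1 and with Table 3, so that all treated subjects are asked to attend the scheduled post-treatment assessments whatever their response or relapse status. Delete the exemption in 6.4.2, and define partial responder or drop it.
2. **Relapse.** State that relapse ends the time-to-relapse endpoint but not the scheduled assessments. Make the relapse denominator all subjects who met the response definition during the treatment period, in line with 2.1, 4.1 and 6.4.2. Restricting it to week-24 responders would change the documented population.
3. **Analysis set.** In 7.2, name all treated subjects as the denominator for responder proportions. Count missing as non-response (one reasonable choice), show the number measured, and give best-case and worst-case bounds. Classify relapsers by measured SALT, and report the number measured beside each mean.
4. **Timing.** Anchor post-treatment endpoints in 2.2, 6.4.2 and 7.3 to 12 and 24 weeks after end of treatment, as Table 3 does.

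**Cost.** The changes are to wording, and no new visit is added to the schedule. Each nonresponder who would otherwise leave attends two visits already in Table 3 (up to 9 subjects in the illustration), and relapsers attend any that remain (2 subjects). The downsides are visit burden, possible understatement of delayed response when refusals count as non-response, and an apparent prolongation of the 5.5.1 medication prohibition for nonresponders and relapsers. The sponsor must reconcile that last point; no clinical rule is proposed here.
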